## 7. Overall study design and plan

The study is conducted as an open, prospective observational study on an outpatient basis. After giving the Informed Consent subjects will be screened at Visit 1. Subjects meeting the inclusion and exclusion criteria will be included (phase 1). If subjects agree to receive VIT, side effects during the buildup phase will be recorded (phase 2). At the first annual control visit side effects during maintenance phase and, if applicable, the outcome of field stings of sting challenge tests will be recorded (phase 3). No additional study-related visits are required.

Participation in this study will have no influence on decision-making for venom-immunotherapy. All procedures have to be in concordance with current EAACI guidelines, and will be conducted individually by each study center.

Detailed schedule of events please see Table 2.

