## 1. Study synopsis

APPLICANT / COORDINATING INVESTIGATOR	[name], PhD Department of Dermatology Medical University of Graz [name] [name], Austria [contact] Telefax: [contact] E-mail: [contact]
TITLE OF STUDY	The effect of antihypertensive drugs on severity of anaphylaxis and side-effects during venom immunotherapy
SHORT TITLE	EADOAS-Study
POPULATION	Patients with a history of anaphylactic sting reaction
OBJECTIVE(S)	The primary objective of this study is to evaluate whether subjects under antihypertensive treatment with beta-blockers and/or ACE-inhibitors show more side effects during VIT compared to subjects with no antihypertensive treatment.
INTERVENTION(S)	Venom immunotherapy (VIT)
KEY INCLUSION AND EXCLUSION CRITERIA	Inclusion criteria: Subjects aged from 35 to 85 years with a history of anaphylactic sting reaction  Exclusion criteria (only for phase 2): Absolute contraindications for VIT, Pretreatment with Omalizumab
OUTCOME(S)	Proportion of side-effects during venom immunotherapy
STUDY TYPE	Prospective multicenter observational study
STATISTICAL ANALYSIS	The primary analysis will compare the proportion of objective side effects between the groups (subjects under antihypertensive treatment vs. subjects without antihypertensive treatment) using a Mantel-Haensel estimate of the odds ratio stratified by clinic.  A logistic regression model will be used to control for other possible confounders
ETHICAL APPROVALS	Participating study centers have to obtain ethical approvals from their institutional review boards.
SPONSORING	Unrestricted grants from pharmaceutical companies
SAMPLE SIZE	1319
TRIAL DURATION	July 1, 2014 – December 31, 2019 (End of inclusion phase: January 31, 2018)

PARTICIPATING CENTERS	Name	Address	Country
	[name] [name], MD, PhD	Department of Dermatology Medical University of Graz [name] [name], Austria	Austria
	[name], MD	Clinical Department of Dermatology Medical University of Innsbruck [name] [name], Austria	Austria
	[name]	Department of Dermatology SALK Paracelsus Medical University Salzburg [name] [name], Austria	Austria
	Prim. Univ.-Doz. [name]	Department of Dermatology Elisabethinen Hospital Linz [name] [name], Austria	Austria

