### 6.3 Exclusion criteria for phase 2 (no exclusion criteria for phase 1)

- Absolute contraindications for VIT
- Pretreatment with Omalizumab

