## 6.4 Methods

### 6.4.1 Personal history

6.4.2 Personal history is recorded at Visit 1 if patients have met inclusion and exclusion criteria. Previous sting reactions, allergies, diseases and current medication will be recorded in the CRF.

Symptoms will be divided into subjective and objective symptoms. Subjective symptoms are: feeling of warmth, isolated pruritus, headache, general fatigue, anxiety, dysphagia, throat tightness, chest tightness, nausea, vertigo, perception of impending doom

Objective symptoms are: flush, urticarial, angioedema, dyspnea, hoarseness, drop in blood pressure, tachycardia, vomiting, abdominal cramping, bronchospasm, involuntary urination, involuntary defecation, loss of consciousness, cardiac arrest, apnoea

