## 8. Schedule of study procedures

### ***Phase 1 (Screening, inclusion) – Visit 1. (week 0)***

The following procedures will be performed:

- Ask the subject to read and sign the Informed Consent
- Review of inclusion and exclusion criteria
- Collect medical and allergy history, recording of co-medication
- Collect demographics
- Perform skin testing and determination of IgE and serum tryptase (CAP)
- Record decision regarding venom immunotherapy (yes/no)

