**13.2 Table 2**

Study procedures	Visit 1	Visit 2	Visit 3/3a	Visit 3b/c a
	Screening/Inclusion	Up-dosing	Maintenance Phase	Field sting / sting challenge
Informed consent	X			
Inclusion/Exclusion review	X			
Allergy history	X			
Medical history / co-medication	X	X	X	X
Demographics	X			
Collect results of IDT and CAP	X			
Recording of decision regarding venom immunotherapy (yes/no)	X			
Recording of venom used for VIT		X		
Recording of side-effects		X	X	
Recording of stinging insect				X
Recording of sting reaction				X

a if applicable.

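### Sections 7 and 6.4.1 apply to phase 1 the exclusion criteria that Section 6.3 and the synopsis reserve for phase 2, so centers can assemble different phase 1 populations

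*Combined protocol and SAP*

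**What the plan says.** **Scope of the exclusions.** The heading of Section 6.3 reads "Exclusion criteria for phase 2 (no exclusion criteria for phase 1". It lists two criteria, "Absolute contraindications for VIT" and "Pretreatment with Omalizumab". The synopsis agrees on scope: "Exclusion criteria (only for phase 2".

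**Entry and history.** Section 7 describes enrollment this way: "Subjects meeting the inclusion and exclusion criteria will be included (phase 1". Section 6.4.1 says: "Personal history is recorded at Visit 1 if patients have met inclusion and exclusion criteria". That history covers previous sting reactions and current medication.

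**Timing of the check.** Section 8 lists "Review of inclusion and exclusion criteria" among the phase 1 procedures at Visit 1. Table 2 has a row "Inclusion/Exclusion review" marked under Visit 1 and under no other visit.

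**Use of the data.** Two secondary objectives in Section 5.2 concern the severity of sting reactions, one by antihypertensive treatment and one by cardiovascular disease or hypertension. Section 11 names a single analysis population, the patients who completed buildup, and does not separate the side-effect analyses from the sting-severity analyses.

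**The concern.** For a patient with an absolute contraindication to VIT, or with prior omalizumab, the entry rule depends on which section a center follows. Under 6.3 and the synopsis the patient belongs in phase 1. Under Section 7 the patient does not, and Section 6.4.1 makes no provision for recording that patient's history.

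At stake is who forms the phase 1 population for the sting-severity objectives. Prior sting reactions and medication are collected at Visit 1, and history that a center did not record cannot be recovered later from the study data. The primary analysis is stratified by center, but the tests for secondary endpoints in Section 11.2 are not, so a difference in enrollment practice between centers would pass into those comparisons unadjusted.

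**Working it through.** **1. What the plan expects phase 1 to contain.** Section 11.3 gives 831 evaluable patients, 30% who do not start immunotherapy and 10% who do not finish.

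- Retained share: (1 − 0.30) × (1 − 0.10) = 0.63, so drop-out is 37%, as stated.
- Enrolled: 831 / 0.63 = 1319.05, which reproduces the stated 1319.
- Not starting VIT: 0.30 × 1319 = 395.7, about 396 patients.

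Phase 1 is thus planned to hold several hundred people who never receive VIT. Visit 1 also records the VIT decision as yes or no. Both facts suggest that the scope given in 6.3 is deliberate.

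**2. The provisions side by side, for a patient who meets an exclusion criterion.**

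| Provision | Enters phase 1? | Visit 1 history recorded? |
|---|---|---|
| Section 6.3, synopsis | Yes | Nothing prevents it |
| Section 7 | No | Not reached |
| Section 6.4.1 | Not addressed | Provided for only where both sets of criteria are met |
| Section 8, Table 2 | Review scheduled; consequence not stated | Listed without a condition |

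Section 7 contradicts 6.3 directly, and 6.4.1 is hard to square with it. Section 8 and Table 2 do not contradict 6.3. They leave open what the Visit 1 review decides.

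**3. Primary endpoint.** It concerns side effects during VIT. On either reading these patients are outside phase 2, so the phase 1 entry rule does not change it.

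**4. Number of patients.** The documents give no share for either criterion. As an assumption only, shares of 1% and 10% would be 0.01 × 1319 ≈ 13 and 0.10 × 1319 ≈ 132 patients.

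**5. Effect on an odds ratio for severe sting reactions.** Let x₁ and y₁ be the proportions removed among severe and mild reactors on the drugs, and x₀ and y₀ the same among those not on them. Then

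OR(observed) = OR(true) × [(1 − x₁)(1 − y₀)] / [(1 − y₁)(1 − x₀)].

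If removal depends on drug use but not on sting grade, x₁ = y₁ and x₀ = y₀, and the factor is exactly 1. If it depends on grade but not on drug use, x₁ = x₀ and y₁ = y₀, and the factor is again 1. It departs from 1 only when removal depends on both jointly, and it can then lie on either side of 1. The documents supply none of the four proportions.

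**6. Effect under the analysis population as written.** Section 11 read literally keeps the buildup completers, planned at 831. The other 1319 − 831 = 488 enrolled patients fall out of every analysis, including those of sting severity. Patients who meet an exclusion criterion are among those left out whichever entry rule a center applies.

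**The case against.** The best defense is that the sections can be read together. The criteria are defined once, in 6.3, with their scope stated there and confirmed in the synopsis. Section 7 may simply refer back to that definition, under which there is nothing to fail at phase 1. A Visit 1 check is also natural: the VIT decision is recorded then, and Visit 2 comes only after the maintenance dose is reached, so no other scheduled visit precedes treatment. Section 6.4.1 says that history is recorded if the criteria are met. It does not say that it is withheld otherwise.

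Part of this stands. Section 8 and Table 2 alone would be no more than unclear, and nothing shows that any center will turn such patients away. It does not clear Section 7, which names the exclusion criteria as a condition and attaches that condition to phase 1. A center working from the design and schedule sections would have good reason to apply it.

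A reader might also infer that the sting-severity odds ratio will be biased, probably toward no effect, because contraindicated patients are more often on these drugs or have cardiovascular disease. The documents do not support that. They do not list the absolute contraindications, and Section 3.1.3 describes the contraindication concerning beta-blockers as relative. A link with drug use alone leaves the odds ratio unchanged (step 5), and no joint link with sting grade is given.

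**Conclusion.** The contradiction is real and stands in current text. Section 7 conflicts with Section 6.3 and the synopsis on phase 1 entry, Section 6.4.1 conflicts with them on history, and Section 8 and Table 2 do not settle the matter. The consequence is that the phase 1 population for the secondary sting-severity objectives may be defined differently from center to center.

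The point reaches no further than that. The primary endpoint is untouched by the phase 1 entry rule. The number of patients concerned is not derivable; 13 to 132 rests wholly on an assumed 1% to 10%. The size and direction of any bias are not derivable either. Under Section 11 as written the patients in dispute are in no analysis at all, so the entry rule and the analysis population have to be settled together.

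**What to change.** - **Sections 7 and 6.4.1:** rest phase 1 entry and the recording of Visit 1 history on the inclusion criteria only, in line with 6.3 and the synopsis. Suggested sense: *Patients who fulfill the inclusion criteria enter phase 1 and have their history recorded; the criteria in 6.3 govern entry to phase 2 alone.*
- **Section 8 and Table 2:** separate the inclusion review from the exclusion review and label the latter as applying to phase 2. Note its result at Visit 1 alongside the VIT decision, and confirm it from the pre-treatment and co-medication data already collected at Visit 2. Table 2 has no visit at the start of VIT, and none needs to be added.
- **Section 11:** limit the buildup-completer population to the analyses of VIT side effects, and state that the sting-severity analyses use all phase 1 patients. Without this, the entry-rule change alters no analysis.

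The cost is wording in these sections and one additional analysis set. No visit or test is added, and decisions about VIT stay with the centers, as Section 7 already provides.

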## 8. Schedule of study procedures

### ***Phase 1 (Screening, inclusion) – Visit 1. (week 0)***

The following procedures will be performed:

- Ask the subject to read and sign the Informed Consent
- Review of inclusion and exclusion criteria
- Collect medical and allergy history, recording of co-medication
- Collect demographics
- Perform skin testing and determination of IgE and serum tryptase (CAP)
- Record decision regarding venom immunotherapy (yes/no)

### ***Phase 2 (up-dosing of VIT) – Visit 2. (0-4 weeks after reaching maintenance dose)***

- Re-collect medical history, recording of co-medication
- Record of up-dosing scheme and of the respective venom used for VIT
- Record pre-treatment during VIT
- Record of side-effects during VIT up-dosing

***Phase 3 (maintenance phase) – Visit 3/3a (at least 12 months [+/- 2 months] after reaching maintenance dose)***

- Re-collect medical history, recording of co-medication
- Record of side-effects during VIT maintenance phase

***Phase 3 (maintenance phase) – Visit 3b/3c optional***

- Document field stings and sting challenges
- Record outcome of field sting or sting challenge

## **9. Early termination of study**

The subject will be advised in the Informed Consent Form that he/she has the right to withdraw from the trial at any time without prejudice. Reasons for a premature treatment stop will be documented, if feasible.

The enrolment of new subjects will be suspended if more than 5 serious anaphylactic reactions ( $\geq$ grade III according to Ring & Messmer; except bronchoconstriction) during buildup phase in patients with antihypertensive treatment occur.

## **10. Data recording and documentation**

Data are recorded in case report forms (CRFs). Data will also be collected using a web based form. Data regarding this study is recorded, analyzed, and archived in anonymized form.

## **11. Statistical methods**

All patients who participate in this study belong to one of the following two groups for the analyses: the group without antihypertensive medication, and the group on antihypertensive medication (beta blockers and/or ACE inhibitors). The analyses will be based on the patients who completed buildup phase of immunotherapy.

Categorical variables will be described with percentages, and continuous variables will be expressed as means  $\pm$  standard deviation or median with interquartile range.

Statistical analysis will be performed using IBM SPSS Statistics 21. A 5% level of significance will be used throughout. In all analyses, an appropriate transformation may be used to obtain approximate normality.

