### **11.1 Analysis of primary endpoint**

The primary endpoint for the study is the presence of objective side effects during immunotherapy which is defined as binary outcome: yes if any grade of objective side effect occurred, no otherwise.

The primary analysis will compare the proportion of objective side effects between the groups using a Mantel-Haensel estimate of the odds ratio stratified by center. A logistic regression model will be used to control for other possible confounders: age, gender, cardiovascular disease, hypertension, chronic bronchial disease or asthma, total IgE, venom-specific IgE, tryptase levels, mastocytosis, skin test reactivity, and study centers.

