### **11.3 Sample size**

It is assumed that 24% of the patients will be on beta blockers and/or ACE inhibitors. A  $\chi^2$  test with a two-sided 5% significance level has a 80% power to detect the difference between the group without antihypertensive medication with 6% side effects during VIT and the group on beta blockers and/or ACE inhibitors with 12.3% side effects during VIT (OR = 2.2) when the sample sizes are 631 and 200 (a total sample size of 831), respectively.

The drop-out rate includes study dropouts (30%) who do not start immunotherapy and study dropouts (10%) who do not end immunotherapy. This results in a drop-out rate of 37% and a required number of 1319 patients.

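### Restricting the primary analysis to build-up completers drops patients whose primary event made them stop venom immunotherapy

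*Combined protocol and SAP*

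**What the plan says.** Section 11 (Statistical methods) defines one population for all analyses: "The analyses will be based on the patients who completed buildup phase of immunotherapy". Section 11.1 defines the primary endpoint as objective side effects during immunotherapy, scored "yes if any grade of objective side effect occurred, no otherwise". It does not require that build-up be completed. Sections 11.1 and 11.2 name no other analysis set and no sensitivity analysis.

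Section 11.3 removes two kinds of dropout before arriving at the analysed sample: 30% who never start VIT, and "study dropouts (10%) who do not end immunotherapy".

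On data collection, section 7 states the intention: "If subjects agree to receive VIT, side effects during the buildup phase will be recorded". Section 8 assigns this task ("Record of side-effects during VIT up-dosing") to Visit 2, which is scheduled "0-4 weeks after reaching maintenance dose". The next side-effect record is at Visit 3/3a ("Record of side-effects during VIT maintenance phase"). Table 2 marks the row "Recording of side-effects" at Visits 2 and 3/3a only. Section 9 asks that reasons for a premature treatment stop be documented where feasible. It does not ask for the side effects themselves.

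**The concern.** A reaction during build-up is an obvious reason to stop VIT, and it is also the primary event. Conditioning on completion therefore selects patients on a possible consequence of the outcome.

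- If reactors stop more often than non-reactors, the side-effect rates are understated.
- If reactors stop at different rates in the two groups, the OR is biased as well.

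The protocol's own rationale makes unequal stopping plausible. Sections 3.1.2 and 3.2.2 suggest that reactions under these drugs may be more serious or harder to treat, and severity may influence who stops. That is an inference, since the documents contain no data on it.

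The visit schedule compounds the problem. A patient who never reaches maintenance dose has no stated point at which build-up side effects are entered. If they are not captured at the time, the exclusion may be hard to examine or correct later.

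**Working it through.** **Reproducing the plan's figures.** Inputs from section 11.3: 6% vs 12.3%, groups of 631 and 200, two-sided 5%, dropout of 30% and 10%.

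- OR = (0.123/0.877)/(0.06/0.94) = 2.197.
- Power of the χ² test (pooled variance under the null, no continuity correction) = 79.96%, matching the stated 80%.
- Dropout: 1 − 0.70 × 0.90 = 0.37, and 831/0.63 = 1319.

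The sample-size arithmetic is sound.

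**Starters and events.** 1319 × 0.70 = about 923 starters. If 24% are exposed among starters too, that is about 701 unexposed and 222 exposed. If 6% and 12.3% are rates among starters, expected reactors are 701 × 0.06 + 222 × 0.123 = 42.1 + 27.3 = 69.4.

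**Effect of the completer restriction.** Let s0 and s1 be the shares of unexposed and exposed reactors who stop in build-up; these are assumptions. Non-reactors stop at one common rate in both groups, set so that 10% of all starters stop in build-up. Then

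completer OR = 2.197 × (1 − s1)/(1 − s0).

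| s0 / s1 | Completer rates (unexposed / exposed) | OR | Power | Reactors lost |
|---|---|---|---|---|
| 10% / 10% | 6.0% / 12.3% | 2.20 | 80% | 6.9 |
| 20% / 20% | 5.3% / 11.0% | 2.20 | 76% | 13.9 |
| 5% / 15% | 6.3% / 11.7% | 1.97 | 68% | 6.2 |
| 15% / 5% | 5.7% / 12.9% | 2.46 | 88.5% | 7.7 |
| 10% / 30% | 6.0% / 9.8% | 1.71 | 46% | 12.4 |
| 30% / 10% | 4.7% / 12.2% | 2.83 | 93% | 15.3 |

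The first row is the neutral case: reactors and non-reactors stop alike and nothing changes except the sample size already planned for.

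**Does the meaning of the 10% matter?** Section 11.3 refers to not ending immunotherapy, and VIT is followed into maintenance, so the 10% may include later dropouts. With only 5% stopping in build-up, the ORs are identical (the formula does not contain the total). Power is 76%, 46% and 93% for 20/20, 10/30 and 30/10, so the result does not rest on how the 10% is split.

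**Scale.** With 631 × 0.06 = 37.9 and 200 × 0.123 = 24.6 events, the standard error of the log OR is √(1/37.9 + 1/593.1 + 1/24.6 + 1/175.4) = 0.273. The planned 95% interval around 2.2 is then about 1.29 to 3.75. Every OR in the table lies inside it, so the observed OR alone would not reveal the bias.

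**All starters instead.** With 701 and 222 patients at 6% and 12.3%, power is 83.5%.

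**The case against.** **The recording gap is partly covered.** Section 9 suspends enrolment after more than five serious build-up reactions in patients on antihypertensives, which presupposes that these are reported whether or not maintenance is reached. Section 7 intends to record build-up side effects for all who agree to VIT, Table 2 labels Visit 2 simply as up-dosing, and centers hold routine records. This stands in part: later retrieval is plausible, so the data need not be lost. But the suspension rule covers only grade III or higher reactions (bronchoconstriction excepted) in exposed patients, while the endpoint counts any grade in both groups. No trigger for completing the form in early stoppers is stated.

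**The power figures depend on a reading.** Section 11.3 attaches 6% and 12.3% to the 631 and 200 analysed patients. If these are completer rates, the completer analysis has 80% power by construction and the losses in the table do not apply. This stands. The OR shifts do not depend on that reading, although they do need the common stopping rate for non-reactors.

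**The remedy has its own bias.** A non-reactor who stops early for other reasons counts as a no after short exposure. Let w be the share stopping for other reasons and f the share of risk still ahead, so that the rates become 0.06(1 − w0·f) and 0.123(1 − w1·f). With w = 5% / 15% (unexposed / exposed) and f = 1, the all-starters OR is 1.93; with 15% / 5% it is 2.46. With f = 0.5 they are 2.07 and 2.32; with equal 10% / 10% and f = 1 it is 2.18. At f = 1 these shifts are about as large as those from completer selection at the same contrasts. The point stands as a reason to report both sets. Neither analysis alone shows which mechanism is at work.

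**Conclusion.** The concern holds. On the text, sections 11 and 11.1 together exclude patients who have the primary event and stop build-up because of it, and nothing elsewhere in the documents corrects this. That reading is firm.

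The effect on the result is not established, because the documents give no stopping rate, overall or by group. Under the assumed contrasts the OR moves from 2.20 to between 1.71 and 2.83, in a direction that cannot be predicted; equal stopping among reactors leaves it unchanged. The power figures of 46% to 93% apply only if 6% and 12.3% are rates among starters. This should be fixed: the size is unknown, but the flaw concerns the primary analysis and is cheap to remove.

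**What to change.** - **Section 11:** make the primary set all patients who received at least one VIT injection. Count any objective side effect up to the end of the endpoint period in section 11.1 or, in early stoppers, up to and including reactions to the last injection.
- **Section 8 and Table 2:** state that the Visit 2 side-effect record is completed when VIT is stopped before maintenance dose.
- **Sensitivity analysis and reporting:** keep build-up completers as a sensitivity analysis. Report by group how many stopped in build-up and how many of these had an objective side effect. The completer analysis is free of the short-exposure problem but still carries the selection on outcome, so it must be read with these counts.
- **Section 11.3:** keep enrolment at 1319 and note about 923 expected starters (about 701 and 222). Quote 83.5% power only with the stated assumption that 6% and 12.3% are rates among starters. If they are completer rates, the planned 80% belongs to the completer analysis, and power among starters depends on the unknown stopping rates.

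The cost is wording in the analysis plan and an existing form completed at premature stop, where reasons are already sought. No extra patients are needed. The remaining drawback is the short exposure of non-reacting early stoppers.

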### 3.1.3 Current recommendations

There is good evidence in the literature that anaphylaxis is not more frequent in patients receiving beta-blockers. On the other side patients may be at increased risk from more severe systemic reactions and from ineffective emergency treatment. Therefore there is still a relative contraindication for beta blockers in subjects allergic to hymenoptera venom.

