### 5.2 Secondary objectives

- To evaluate whether subjects under antihypertensive treatment with beta-blockers and/or ACE-inhibitors have more severe sting reactions.
- To correlate the prevalence of cardiovascular diseases and/or hypertension with the risk for more severe systemic sting reactions and with more severe and more frequent side effects under VIT.
- To evaluate whether bee venom is associated with a higher frequency of side-effects.
- To evaluate whether high sIgE levels are correlated to a higher frequency of side-effects.
- To evaluate whether high tryptase levels are correlated to a higher frequency of side-effects.
- To evaluate whether quicker up-dosing protocols are correlated to a higher frequency of side-effects.
- To evaluate efficacy of VIT by sting challenges or field stings and look for differences between patients with and without antihypertensive treatment

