### **11.2 Analysis of secondary endpoints**

For the analysis of secondary endpoints, comparison between groups will be made by using  $\chi^2$  statistics or the Fisher exact test for categorical variables and by t-test or the Mann-Whitney U test for continuous variables.

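### Section 11 restricts every analysis to patients who completed VIT build-up, so the sting-severity objectives lose about 37% of the patients enrolled at Visit 1

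*Combined protocol and SAP*

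**What the plan says.** The general part of section 11 assigns patients to two groups (with and without beta-blockers and/or ACE inhibitors) and then fixes the population: "The analyses will be based on the patients who completed buildup phase of immunotherapy". The sentence carries no exception and precedes both the primary and the secondary analysis sections. Section 11.2 begins "For the analysis of secondary endpoints, comparison between groups will be made by using" and lists tests, but no population.

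Two secondary objectives in section 5.2 concern the severity of sting reactions rather than of VIT side effects. The first is "To evaluate whether subjects under antihypertensive treatment with beta-blockers and/or ACE-inhibitors have more severe sting reactions". The second opens with "To correlate the prevalence of cardiovascular diseases and/or hypertension with the risk for more severe systemic sting reactions" and goes on to side effects under VIT.

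The data for the sting-severity comparisons are taken early. Sections 6.4 and 8 have previous sting reactions, diseases and current medication recorded at Visit 1, together with the decision for or against VIT. Section 7 places enrolment at that point: "Subjects meeting the inclusion and exclusion criteria will be included (phase 1"). The title of section 6.3 reads "Exclusion criteria for phase 2 (no exclusion criteria for phase 1"), so absolute contraindications to VIT and omalizumab pretreatment apply only to phase 2. Entry to phase 2 depends on the patient agreeing to VIT.

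Section 11.3 plans for "study dropouts (30%) who do not start immunotherapy and study dropouts (10%) who do not end immunotherapy", a combined loss of 37%, with 1319 enrolled and 831 analysed.

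**The concern.** For VIT side effects, an analysis set defined by VIT is natural. For sting severity it is not: outcome and exposure are both recorded before VIT, and whether the patient later starts or finishes VIT is no part of the question. Patients who decline VIT, are excluded from phase 2 or stop during build-up are enrolled, have their sting history taken, and are then left out.

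Two things are at stake. The first is precision, which follows directly from the plan's own figures. The second is the possibility of selection: completing VIT comes after both the sting reaction and the drug exposure. If it depends on the two jointly, the odds ratio among completers differs from that in the enrolled cohort. Section 11.2 offers only simple group comparisons for secondary endpoints, which would neither reveal nor address this.

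Sting severity is not incidental to the study. It is the first question raised in section 2, and section 4 rests its promise of a clear statement on 1319 patients, 317 of them on the drugs.

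**Working it through.** **Inputs from the plan (sections 4 and 11.3).** 30% do not start VIT; 10% do not finish; 24% on beta-blockers and/or ACE inhibitors; 631 and 200 patients analysed; 6% versus 12.3% side effects; two-sided 5%; 80% power; 1319 enrolled.

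**1. Reproducing the plan's figures.** Chi-square test with pooled variance under the null, no continuity correction:

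- Pooled proportion = (631 × 0.06 + 200 × 0.123)/831 = 0.0752.
- SE under the null = √[0.0752 × 0.9248 × (1/631 + 1/200)] = 0.0214.
- SE under the alternative = √[0.06 × 0.94/631 + 0.123 × 0.877/200] = 0.0251.
- z = (0.063 − 1.96 × 0.0214)/0.0251 = 0.84, so power is 79.96% (stated: 80%).
- Odds ratio = (0.123/0.877)/(0.06/0.94) = 2.197 (stated: 2.2).
- Retention = 0.70 × 0.90 = 0.63, a loss of 37%; 831/0.63 = 1319.05 (stated: 1319).

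The plan's figures reproduce. They also show that the 10% applies to those who start VIT.

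**2. Patients lost to the sting-severity objectives.**

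- Enrolled minus analysed: 1319 − 831 = 488, and 488/1319 = 37.0%.
- Never start VIT: 1319 × 0.30 ≈ 396.
- Start but do not finish: 1319 × 0.70 × 0.10 ≈ 92.

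**3. Loss of precision.** At 24% exposed, the full cohort splits into about 1002 and 317 (the 317 is given in section 4); the completers split into 631 and 200. For the same underlying proportions the ratio of standard errors is √(1/631 + 1/200) / √(1/1002 + 1/317) = 0.0811/0.0644 = 1.26. The shortcut √(1319/831) also gives 1.26.

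**4. Detectable odds ratio.** The documents give no rate of severe sting reactions, so the rate in untreated patients is an assumption, shown over a range. Same test and formula as in step 1, solved for 80% power:

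| Assumed severe rate, untreated | Detectable OR, all 1319 | Detectable OR, 831 completers |
|---|---|---|
| 10% | 1.70 | 1.92 |
| 20% | 1.52 | 1.69 |
| 30% | 1.46 | 1.61 |
| 40% | 1.44 | 1.58 |

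An effect that 831 patients detect with 80% power would be detected with about 94% power in all 1319.

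**5. Selection.** Let r be the probability of completing build-up. With a true odds ratio of 1, the odds ratio among completers is

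(r severe, treated / r mild, treated) ÷ (r severe, untreated / r mild, untreated).

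It departs from 1 only if the severe-to-mild ratio of retention differs between the drug groups. All rates below are assumed. Untreated patients have 0.80 (severe) and 0.60 (mild) throughout; overall retention is 60% to 63% if 20% to 30% of reactions are severe.

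| Retention in treated patients, severe / mild | OR among completers |
|---|---|
| 0.64 / 0.48 (multiplicative effects) | (0.64/0.48)/(0.80/0.60) = 1.00 |
| 0.80 / 0.40 | (0.80/0.40)/(0.80/0.60) = 1.50 |
| 0.55 / 0.55 | (0.55/0.55)/(0.80/0.60) = 0.75 |

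The illustrations fall on both sides of 1, and the documents give no basis for choosing among them.

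**The case against.** **The sentence may have been meant only for VIT endpoints.** Section 11 does say that all participating patients belong to one of the two drug groups. But that assigns groups; the sentence after it fixes the analysis set, without exception. An analyst following the text would drop these patients, so it needs changing even if the intention was different.

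**The effect on the conclusions is limited.** The primary endpoint and the sample size are untouched by this point. The affected objectives are secondary, the plan claims no power for them, and only half of the second one is involved. All of this stands, and it bounds the importance of the point.

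**The 37% is a planning assumption.** This also stands. Nor do the documents promise that severity will be fully recorded for all 488; they say only that previous sting reactions are recorded at Visit 1.

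**A stronger reading is tempting.** A reader might infer that completing VIT must depend on both drug use and sting severity, so that the completers' odds ratio is biased, perhaps upwards. The documents do not support this:

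- Section 3.1.3 says "Therefore there is still a relative contraindication for beta blockers in subjects allergic to hymenoptera venom". As worded, this concerns the drug, not withholding VIT. Section 3.2.3 likewise speaks of replacing ACE inhibitors.
- Section 6.3 bars only absolute contraindications from phase 2, and section 3.1.2 describes VIT as common in older patients, who are more likely to take beta-blockers.
- No section says that severity drives the decision for VIT, however plausible that is.
- Even if both links held, multiplicative effects on retention would leave the odds ratio unchanged (step 5).

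**Conclusion.** The point holds as one about the analysis set. As written, section 11 removes about 488 of 1319 patients (37%) from the sting-severity objective by drug group and from the sting-severity half of the cardiovascular objective, although their outcome and exposure are due to be recorded before VIT. The standard error is about 1.26 times larger than it need be. The size rests on the plan's 30% and 10% loss assumptions and on 24% exposure both among those enrolled and among completers, as sections 4 and 11.3 have it. The detectable odds ratios rest in addition on an assumed severe rate of 10% to 40%.

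It also rests on reading these objectives as concerning the sting history taken at Visit 1. That is the natural reading, since field stings and sting challenges have their own objective in section 5.2.

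Selection bias is possible, conditional on severity and drug use acting non-multiplicatively on starting or completing VIT, and of unknown direction and size. It should not be presented as established. Whether completers are the right set for the side-effect endpoints themselves is a separate question.

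**What to change.** In section 11, replace the single population by sets named per objective:

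- Limit the build-up set to the VIT side-effect endpoints. The efficacy objective also needs patients who received VIT and is not affected by this point.
- Analyse sting-reaction severity, by antihypertensive treatment and by cardiovascular disease or hypertension, in all patients included at Visit 1 with a recorded sting reaction, whether or not VIT is started or completed. Completers should serve at most as a sensitivity analysis.
- Tabulate the VIT decision, already recorded at Visit 1, by drug group and sting-reaction grade, so that readers can see whether uptake differs jointly by the two.

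The cost is a sentence or two in section 11 and one additional table. It needs no new data, visits or patients.
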